## **R21 Environmental Enrichment Study Protocol**

*Translation of the EE intervention:* The environmental enrichment (EE) paradigm was translated by a multidisciplinary team composed of investigators with expertise in psychology, physiology, neuroscience, integrative mind-body disciplines, gynecology, and translational research, together with consultants in HPA axis research and stress management, met during a period of one year to design an intervention to be tested in patients. A pilot randomized clinical trial was designed to test the efficacy of reducing painful symptoms and improving QoL as an adjuvant to standard care. The adaptation followed the ORBIT Model proposed by Czajkowski *et al.* (2015) to develop behavioral interventions for chronic diseases [refs]. This model guides the early pre-efficacy stages of the development of a behavioral intervention using a four-phase approach (F1: design, F2: preliminary efficacy, F3: efficacy, F4: effectiveness (F2 to be tested in the current proposal). Guided by the model, we translated a basic neurobehavioral finding (*stress control and EE reduces the growth of lesions in rats*) into a clinical question (*will an EE intervention be effective in reducing pain symptoms/inflammation and increasing QoL in women with endometriosis?*). First, we conducted a systematic literature review to select the approaches for the adapted EE intervention, using the PRISMA-P 2015 protocol and the PRISMA evaluation checklist. The process of translating the environmental enrichment (EE) paradigm has been described in detail in Nieves-Vázquez et al. (2022) [41].

**Recruitment**: After IRB approval (Protocol #1901004205R003) a recruitment campaign was conducted using social media (Facebook, Instagram, Twitter) of the Fundación Puertorriqueña de Pacientes con Endometriosis (ENDOPR), the only patient support association in Puerto Rico established in 2015. Recruitment for session one took place from September 2019 to December 2021 and then from May to June 2021. Recruitment for session two took place from August 2021 to February 2022. Patients interested in participating will be first screened for inclusion/exclusion criteria by our research coordinator and verbally consented to before being randomized into the intervention and control groups described below.

*Inclusion Criteria:* Participants were women with a surgical diagnosis of endometriosis, 18-50 years old, who are symptomatic and refractory to hormonal treatment, able to provide written informed consent, and can commit the time to participate in the environmental enrichment (EE) intervention for a period of 3 months. *Exclusion Criteria:* We excluded patients who present endometriosis symptoms but who have not been diagnosed by surgery by an OB-GYN specialist; pregnant women or those who plan to or become pregnant during the study period; women with endometriosis under hormonal treatment who report no symptoms as defined predominantly by pain; post-menopausal women; documented or visual cognitive or physical impairment that would interfere with participation or consent; currently under mental health treatment or using

steroid medications; affected by other confounding conditions, including pain syndromes (e.g., fibromyalgia, chronic fatigue syndrome, arthritis).

Study design of the pilot RCT: To evaluate the efficacy of a translated EE intervention for endometriosis patients, we conducted a RCT of parallel design with an intervention group (EE intervention) (n=29) and a wait list control group (n=27) from August 2021 to July 2022. Participants randomized to the intervention participated in six EE modules on alternate Saturday mornings. They could receive (or continue receiving) standard gynecological care (hormonal, analgesics, or surgeries) and psychological therapy as needed. Participants randomized to the wait-list control condition were invited to participate in an online seminar about endometriosis and could also receive standard of care for endometriosis and mental health. After providing informed consent, all subjects completed a set of validated surveys at baseline and end of the intervention to assess QoL, perceived stress, anxiety, depression, and pain symptoms, and provided saliva samples. Individuals in the intervention group were followed up 3-months after the study ended to assess possible longterm effects of the intervention. Participants in the control group completed the same questionnaires and provided the saliva samples during house visits that took place within one week before and one week after the timeline of the intervention. Clinical and socio-demographic data, as well as pain catastrophizing scores were obtained with the Endometriosis Phenome Project (EPHect) questionnaire [42]. Participants in the intervention group used WhatsApp chats to continue their communications between meetings. Data regarding treatments and doctor's visits during the study were obtained from all participants with a clinical history questionnaire administered twice during the study period.

*Study surveys*: Participants in the EE condition completed the following surveys at baseline and end of the intervention, and at 3 months after the intervention was completed. Individuals in the control group completed the same questionnaires only at baseline and end of the study period:

(1) Endometriosis Phenome Project Clinical Minimal Questionnaire (EPQ-M): The validated Spanish version of the EPhect's EPQ-M survey was used to collect cross-sectional, self-reported data. Developed by the World Endometriosis Research Foundation (WERF), this survey standardizes data collection from patients, including demographics, medical history, ob-gyn history, and lifestyle [42]. Different types of pelvic pain (dysmenorrhea, dyspareunia, chronic pelvic pain) are measured using a numerical rating scale from 1 (no pain) to 10 (worse pain) [43].

(2) Endometriosis Health Profile-30 (EHP-30): This survey measures the endometriosis-related health status through 30 items covering five disease-related scales (core questionnaire): pain, control and helplessness, emotional wellbeing, social support, and self-image. EHP-30 has been shown to be sensitive to changes in patient outcomes, making it a useful tool in endometriosis clinical trials. Response categories are rated on a five-point Likert scale (0 to 4). The global QoL score is converted on a scale of 0 to 100, with the lower score representing a better quality of life [44, 45].

(3) Brief Pain Inventory (BPI): This questionnaire measures both pain intensity (minimum, maximum, average, current) using a numerical rating scale (NRS) of 0 to 10, with the highest number representing the worst imaginable pain. This instrument also measures the degree of pain impairment on function regarding general activity, mood, walking, work (including housework and paid work), relationships, sleep, and enjoyment of life. A global pain impact score can be calculated, with the higher score indicating worse impact [46].

(4) Perceived Stress Scale (PSS-14): This self-assessment tool measures the level of perceived stress due to life situations over the past month. It assesses to what extent respondents feel in control of unpredictable or unexpected situations, or conversely, whether they feel out of control and experience stress that leads to discomfort. It consists of 14 items with a response format of a five-point scale (0=never, 1=almost never, 2=occasionally, 3=often, 4=very often). A high total score corresponds to a high level of perceived stress [47].

(5) Anxiety (General Anxiety Disorder-7 (GAD-7): This self-administered questionnaire measures anxiety symptomatology through seven items which are scored from 0 to 3. The cut points of 5, 10, and 15 represent mild, moderate, and severe, respectively [48]. Patients reporting moderate-severe scores in GAD-7 were provided with a referral for psychological services.

(6) Patient Health Questionnaire-8 (PHQ-8): This self-administered questionnaire measures depression symptomatology through eight items which are scored from zero to three. Scores of 5, 10, 15, and 20 represent cut points for mild, moderate, moderately severe, and severe, respectively. [49]. Patients reporting moderate-severe scores in PHQ-8 were provided with a referral for psychological services.

(7) Pain catastrophizing scale (PCS): This scale is part of the EPhect-Q Questionnaire that was completed at baseline. The PCS evaluates three dimensions of catastrophizing: helplessness, rumination, and magnification [50]. The scale has a total score of 52 with items scored from 0 ('not at all') to 4 ('all the time') [51]. A PCS score higher than 30 is considered clinically significant and identifies those with a higher risk of chronicity and disability due to pain [52].

**Saliva sampling and cortisol ELISA:** Saliva samples for cortisol were collected at baseline, end of the intervention, and at the 3-month follow up for the experimental group. Saliva samples (approximately 1-3 mL) were obtained by passive drool into pre-labeled 15 mL tubes. These samples were obtained at the same time of the day (between 8:00-9:00am and at noon, before and after the intervention) to account for circadian variations in cortisol levels. For the control group, samples were collected one week before the start of the intervention and one week after during house visits. Control individuals were asked to collect saliva at the same time as the intervention group, on the same day, and store them at 4°C until collection during visits by the research team. Saliva samples were stored short-term on wet ice during transport to the research laboratory where they were processed and stored at -80°C until analysis. Once in the lab, the saliva samples

were spun down to clear buccal cells, and aliquots stored at -80°C until analysis by ELISA. Cortisol analysis was done using the High Sensitivity Salivary Cortisol Enzyme Immunoassay kit (Salimetrics, State College, PA, cat #130025), validated for the quantitative measurement of salivary cortisol, following the manufacturer's protocol. All samples were assayed undiluted in duplicate on the same assay plate. Cortisol concentrations were calculated based on standard curve, averaged, and reported in mg/dL.

**Statistical analysis:** The pilot trial's acceptability and feasibility were determined by rates of Recruitment, Enrollment, Adherence, Survey completion and Module evaluations.Equivalence of baseline characteristics, as well as between-group differences in clinical-demographics variables and study outcomes were assessed using descriptive and univariate statistics, including T-test or Mann-Whitney test for continuous variables (depending on normality of distribution, as assessed by Shapiro-Wilk test), and Chi-square or Fisher's exact test for categorical variables. Between group differences, as well as changes in the intervention group (from baseline) were evaluated for % improvement. Outcomes were evaluated using repeated two-way analysis of variance and assessed differences in intragroup (baseline vs. end of intervention) and intergroup (intervention vs. control). If findings were significant, we used a Tukey post-hoc test. Clinically meaningful changes in pain were considered when there was a change of three or more points (substantial difference), two to three points in the NRS (moderate difference) or 1 point (minimal difference) [43, 53]. A p value of 0.05 or less was considered statistically significant.

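### Control-arm baseline appears to be taken after allocation, with no masking described, so self-reported baseline may depend on the known arm

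*Combined protocol and SAP*

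**What the plan says.** The order of events has to be pieced together from several headings of the combined protocol and SAP.

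- **Recruitment:** after screening by the coordinator, women are "verbally consented to before being randomized into the intervention and control groups described below". Nothing else is placed ahead of randomisation.
- **Inclusion Criteria:** a participant must be "able to provide written informed consent". No time point is attached.
- **Study design of the pilot RCT:** "After providing informed consent, all subjects completed a set of validated surveys at baseline and end of the intervention". The form of that consent, and its place relative to randomisation, are not given. Controls filled in the questionnaires and "provided the saliva samples during house visits that took place within one week before and one week after the timeline of the intervention". The groups are 29 (intervention) and 27 (wait list), without saying whether these are women randomised, enrolled or analysed.
- **Saliva sampling and cortisol ELISA:** "For the control group, samples were collected one week before the start of the intervention and one week after during house visits". Controls were also asked to match the intervention group's collection time.
- **Statistical analysis:** baseline is used to check that the groups are equivalent, as one time level of the repeated two-way ANOVA, and as the reference for percentage improvement.

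No section describes masking, allocation concealment, or holding back the allocation until baseline is complete.

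**The concern.** A baseline is a clean starting point for change only if it cannot be influenced by the allocation. Here the control baseline is obtained through a procedure that exists only for controls and is timed to the other arm's programme. A woman visited at home as a wait-list control probably knows her arm when she answers. Every efficacy outcome except salivary cortisol is self-reported, and the comparator is an unmasked wait list, so disappointment or expectation could colour the baseline answers.

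Any such colouring goes straight into the estimated effect, because the analysis compares change from baseline between arms. The direction cannot be told in advance: inflated baseline symptoms in one arm make that arm appear to improve more, and understated symptoms do the opposite. The baseline equivalence tests do not protect against this, since they use the same reports.

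A second, weaker route is loss of women between randomisation and baseline. If consent is completed after allocation, refusals could differ by arm, and the unlabelled 29 and 27 do not let a reader rule this out.

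**Working it through.** **Step 1: order of events.** The plan gives no figure on this point to reproduce, so the sections are set side by side.

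| Event | Where | What can be established |
|---|---|---|
| Screening, verbal consent | Recruitment | Before randomisation |
| Written consent | Inclusion Criteria | Ability required; timing not stated |
| Control baseline | Study design; Saliva sampling | At control-only visits, so after assignment |
| Intervention baseline | Study design; Saliva sampling | Not dated relative to randomisation |
| Disclosure of the arm | Nowhere | Not stated |

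The third row is an inference, but a tight one: a visit made only to controls cannot be arranged before it is known who the controls are. No section supports the opposite order.

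**Step 2: what a shifted baseline would do.** Inputs from the documents: group sizes 29 and 27; significance level 0.05. Assumptions: two-sided test (sidedness is not stated); shift d in one arm's mean baseline report, in baseline SDs; within-person correlation rho; equal SDs at both times; no true effect; no carry-over of the shift to follow-up; normal approximation.

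With two time points, the group-by-time contrast of the repeated ANOVA compares mean changes.

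- SD of change = sqrt(2(1 − rho)). At rho = 0.5 this is sqrt(1) = 1.
- SE = SD of change × sqrt(1/29 + 1/27) = 1 × sqrt(0.0345 + 0.0370) = 0.267.
- For d = 0.2: 0.2 / 0.267 = 0.75 SE.
- False-positive rate = Φ(d/SE − 1.96) + Φ(−d/SE − 1.96) = 0.116 at d = 0.2.

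| Shift d (SD) | rho 0.3 | rho 0.5 | rho 0.7 |
|---|---|---|---|
| 0 | 0.050 | 0.050 | 0.050 |
| 0.1 | 0.062 | 0.066 | 0.077 |
| 0.2 | 0.097 | 0.116 | 0.162 |
| 0.3 | 0.158 | 0.202 | 0.305 |
| 0.5 | 0.352 | 0.464 | 0.675 |

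If half of a 0.2 SD shift persisted at follow-up, the net shift would be 0.1 SD and the second row would apply (0.062 to 0.077).

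**Step 3: refusals.** If 10% of one arm declined after allocation and differed from the rest by 0.5 SD (both assumed), that arm's baseline mean would move by 0.10 × 0.5 = 0.05 SD, or 0.05 / 0.267 = about 0.2 SE at rho = 0.5. A stable difference between decliners and stayers would also cancel from the change contrast. This route is secondary.

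**The case against.** The strongest reply is that several tempting readings go beyond the text.

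- *Written consent was taken after randomisation, in conflict with the eligibility rule.* A reader might infer this from the Recruitment wording. The criterion concerns ability to give written consent and fixes no time. Verbal agreement at screening is compatible with a signature before or after allocation, and the consent form, not in the text reviewed here, may settle it. No refusal is reported. This reply stands.
- *Every baseline report was given with the arm known.* The documents support only that control baseline appears to follow assignment. They do not say when allocation was disclosed or when intervention-arm surveys were completed. This also stands, and the point is limited accordingly.
- *Eligibility and randomisation may be up to 23 months older than baseline.* This takes September 2019 to August 2021. The recruitment dates for session one are inconsistent in themselves (a window ending December 2021, followed by one in May to June 2021), and no randomisation date is given. The inference is not supported.
- *The 0.2 SD shift is assumed, and a shift that persists at follow-up would partly cancel.* Correct; the calculation is an illustration, not an estimate of bias.
- *The trial has been run, so its order cannot be changed.* True for data already collected, where the remedy is disclosure.

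None of this removes the core: control-only baseline visits presuppose an assigned arm, and nothing described keeps the woman from knowing it.

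**Conclusion.** The point holds in a limited form. As written, the plan leaves baseline open to reporting that depends on allocation, and it uses that baseline directly in its efficacy analysis. This is more than missing detail, because following the described steps produces the problem.

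The 0.2 SD illustration is enough to roughly double the nominal error rate, although it rests on the shift, correlation and no-carry-over assumptions set out in the working. The actual bias, and its direction, cannot be determined from the documents. The order of assignment and control baseline is inferred from the visit arrangements, and participants' knowledge of the arm from the absence of any masking. Selective refusal after allocation remains an open possibility and should be described only as that.

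**What to change.** Reconcile the Recruitment, Inclusion Criteria, Study design and Saliva sampling sections to one explicit order for each session:

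1. Screening, then written consent signed by every woman.
2. Self-completed baseline surveys finished by every woman.
3. Baseline saliva, before disclosure of the arm where logistics allow.
4. Randomisation, then disclosure.

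Report the number randomised in each arm, including any lost before baseline, and say whether 29 and 27 are women randomised or analysed. For sessions already completed, state the order that was actually followed. Where baseline came after disclosure, name this as a limitation and do not treat baseline as a pre-randomisation measure, whether as the starting point for change or as evidence of group equivalence.

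The cost for surveys is small: they are self-completed and need only be scheduled before arms are known. Saliva is less simple. Control samples depended on home storage and collection by the research team, so identical handling would mean visits to all women (56 at the stated sizes, 29 + 27) or a common session before allocation. That is why the surveys, which carry nearly all the efficacy outcomes, should be moved first.

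### The exclusion for becoming pregnant can remove women after randomisation, no analysis population is defined, and the repeated ANOVA does not adjust for baseline, so analysis as randomised cannot be confirmed

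*Combined protocol and SAP*

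**What the plan says.** All references are to the Combined protocol and SAP.

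- **Exclusion Criteria.** The list includes "pregnant women or those who plan to or become pregnant during the study period". Planning a pregnancy and becoming pregnant are named separately.
- **Recruitment.** Women are screened against the criteria and "verbally consented to before being randomized into the intervention and control groups described below". Eligibility is thus settled before allocation.
- **Study design of the pilot RCT.** The groups are "an intervention group (EE intervention) (n=29) and a wait list control group (n=27"), with no statement on whether these are numbers randomised, completing or analysed. The same paragraph says that "all subjects completed a set of validated surveys at baseline and end of the intervention". The EE arm attends "six EE modules on alternate Saturday mornings". Controls are invited to an online seminar and are assessed at house visits.
- **Statistical analysis.** "Outcomes were evaluated using repeated two-way analysis of variance", comparing baseline with end and intervention with control, followed by Tukey tests if significant. Feasibility is judged by "rates of Recruitment, Enrollment, Adherence, Survey completion and Module evaluations". The section has no analysis population, no intention-to-treat statement and no method for missing outcomes. It does not say what happens to the data of a woman who becomes pregnant.

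**The concern.** Randomisation protects the comparison only if the women analysed are those randomised, in the arms to which they were allocated. An exclusion triggered by an event after allocation can undo that, and nothing in the analysis section puts such women back.

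The outcome model is a second route to the same problem. A classical repeated ANOVA with two time points normally uses only women who have both values. Attendance at the modules is asked of the EE arm alone, so losses need not be balanced. If loss depends on baseline severity, a comparison of changes is biased by regression to the mean.

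The model also has a cost when nobody is lost. A change-score comparison is less precise than a baseline-adjusted one, which matters with 56 women.

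**Working it through.** The documents give no SD, dropout rate, pregnancy count or power calculation, so there is no stated figure to reproduce. Group sizes come from the Study design section. All rates, gaps and correlations below are assumptions.

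**1. When the clause can act.** Current pregnancy and planned pregnancy can be checked at screening. A pregnancy that begins during the study period cannot. As screening precedes randomisation, that part of the clause can act only on women already randomised.

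**2. What the ANOVA estimates.** With two groups, two time points and complete data, the group-by-time interaction is the difference between arms in mean change (end minus baseline). Its F statistic is the square of the two-sample t statistic on the change scores.

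**3. Standard error.** In SD units, √(1/29 + 1/27) = √(0.0345 + 0.0370) = 0.27. This is the SE for end values, and for change scores at correlation ρ = 0.5, where the SD of change is √(2(1 − 0.5)) = 1. At ρ = 0.7 the SD of change is √0.6 = 0.775, so the SE is 0.27 × 0.775 = 0.21.

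**4. Removing a few women from the EE arm.** If k of 29 are removed and their mean outcome differs from that of the retained women by Δ, the arm mean moves by (k/29) × Δ.

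| k | Δ = 1 SD or 1 NRS point | Δ = 3 NRS points |
|---|---|---|
| 1 | 0.03 | 0.10 |
| 3 | 0.10 | 0.31 |
| 6 | 0.21 | 0.62 |

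The plan's own minimal difference on the NRS is 1 point.

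**5. Dropout that depends on baseline.** Assume EE dropout of 35% above the median baseline and 5% below (20% overall), and none in controls. The mean of each half of a standard normal is ±0.798. The retained fractions are 0.5 × 0.65 = 0.325 (upper half) and 0.5 × 0.95 = 0.475 (lower half).

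- Retained EE baseline mean: 0.798 × (0.325 − 0.475)/0.80 = −0.15 SD.
- Change-score bias: 0.15 × (1 − ρ), which is 0.075 SD at ρ = 0.5 and 0.045 SD at ρ = 0.7.
- Simulation of this setting (20,000 trials) gives 0.078 and 0.046 SD for change scores, and 0.003 and 0.001 SD after baseline adjustment.

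Higher scores are worse on the main scales. The retained EE women start lower and drift upward, so the bias makes EE look worse.

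**6. Precision.** Per woman, the change-score variance is 2(1 − ρ) and the baseline-adjusted residual variance is 1 − ρ². Their ratio is (1 + ρ)/2.

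- ρ = 0.5: ratio 0.75, a 25% reduction.
- ρ = 0.7: ratio 0.85, a 15% reduction.

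In the simulation with dropout, the SD of the estimate fell from 0.283 to 0.247 (ρ = 0.5) and from 0.219 to 0.206 (ρ = 0.7). In variance that is 1 − (0.247/0.283)² = 24% and 1 − (0.206/0.219)² = 12%. The gain is slightly below the formula because the slope is estimated and the retained arms differ at baseline.

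**The case against.** A reader might infer that the plan states a complete-pair analysis and that the comparison is therefore not of the groups as randomised. The documents do not support that.

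- **Complete pairs.** The Statistical analysis section is silent on incomplete pairs. Dropping them is the usual behaviour of a classical repeated ANOVA, but here it is an inference from the method's name.
- **Completeness.** The Study design section says that all subjects completed the surveys at both times. If that is literal, and 29 and 27 are the randomised numbers, every pair is complete and there is no attrition bias. The sentence would also be true if 29 and 27 were the women left after removals, and survey completion is itself listed as a rate to be determined. So it does not settle the matter.
- **The pregnancy clause.** It stands in an eligibility list and may be only loosely worded. The documents do not say whether a pregnant woman would stop the modules, stop follow-up or have her data removed. No pregnancy, dropout or removal is reported, and excluding women who plan a pregnancy limits the number affected.
- **Unequal loss.** All women had to be able to commit the time before randomisation. Differential dropout is plausible but not shown.
- **Size and direction.** The assumed bias is well below one standard error and runs against EE. It would reverse if milder cases left. Adjustment removes it only when dropout depends on observed baseline. If loss depends on the unseen end value, the adjusted model is biased too.

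These objections reduce the point from an established bias to a risk. They do not supply the missing analysis population, explain the clause or remove the gain in precision.

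**Conclusion.** The point holds in a limited form. As written, the exclusion can remove randomised women, no analysis population keeps them, and the status of 29 and 27 is unstated. Analysis as randomised therefore cannot be confirmed from the documents, but neither is it shown to have failed.

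Any bias is probably small. Under the assumed baseline-dependent dropout it is about 0.045 to 0.08 SD against EE, or 0.075/0.27 = 0.28 and 0.045/0.21 = 0.21 of a standard error at ρ = 0.5 and 0.7. Removing one to three EE women who differ by 1 SD shifts the arm mean by 0.03 to 0.10 SD, in a direction that cannot be known in advance.

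The case for a baseline-adjusted model does not depend on any loss having occurred. Its variance gain of about 25% or 15% rests only on the assumed correlations. The changes should be made, but nothing here invalidates the trial.

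**What to change.** 1. **Criterion and analysis set.** Limit the exclusion to pregnancy or planned pregnancy at screening. State that all randomised women are analysed in their allocated arm, and that data from women who become pregnant later are collected and kept. Whether such women continue the modules is for the sponsor.
2. **Numbers.** Report, by arm, the numbers randomised, removed after randomisation (with reasons) and analysed, and say which of these 29 and 27 are. The text describes the trial as already conducted, so this is the most useful step if enrolment is closed.
3. **Model.** Replace the repeated ANOVA with a baseline-adjusted analysis of all randomised women: ANCOVA, or a mixed model with baseline means constrained equal across arms. State the missing-data assumption, namely that loss depends only on observed values.
4. **Sensitivity.** Add one analysis that sets outcomes after pregnancy onset to missing.

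The cost is the wording of one criterion, a participant-flow table and a standard model fitted to data already collected. The small downside is that a few scores recorded after pregnancy onset enter the main analysis, which the sensitivity analysis addresses.

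### Baseline pain catastrophizing, which the plan treats as a risk marker, is left out of the outcome analysis: a modest loss of precision in a 29 v 27 trial, not a bias

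*Combined protocol and SAP*

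**What the plan says.** Under *Study surveys*, item (7), the PCS is placed at baseline: "This scale is part of the EPhect-Q Questionnaire that was completed at baseline". The same item says "The scale has a total score of 52 with items scored from 0" to 4, and gives the scale a prognostic meaning: a score above 30 is "considered clinically significant and identifies those with a higher risk of chronicity and disability due to pain".

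*Study design of the pilot RCT* reports that clinical and socio-demographic data, "as well as pain catastrophizing scores were obtained with the Endometriosis Phenome Project (EPHect) questionnaire", without limiting this to one arm. It also says that "all subjects completed a set of validated surveys at baseline and end of the intervention", and, introducing the survey list, "Individuals in the control group completed the same questionnaires only at baseline and end of the study period".

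*Statistical analysis* gives one outcome model: "Outcomes were evaluated using repeated two-way analysis of variance and assessed differences in intragroup (baseline vs. end of intervention) and intergroup (intervention vs. control"), followed by Tukey tests when significant. It names no covariate, ANCOVA or stratification. Baseline characteristics are compared between arms by univariate tests, but nothing in the analysis depends on the result.

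**The concern.** By the plan's own account, baseline PCS carries information about later pain and disability, which is what the pain NRS, the BPI and, in large part, the EHP-30 measure. The value is already in hand, and it is not the same thing as the outcome's own baseline score.

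In a trial of 56 women, two things follow from leaving it out. A chance difference between arms in PCS can shift the estimated arm effect, to the extent that PCS predicts the end score beyond what the model already holds. Outcome variance that PCS could explain also stays in the error term. In addition, testing baseline comparability without saying what follows invites a decision to adjust once the result has been seen. A covariate fixed in advance avoids that.

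**Working it through.** **Inputs from the documents.** n = 29 and 27 (*Study design of the pilot RCT*); PCS total 0–52 at baseline (*Study surveys*, item 7); outcome model of visit by arm (*Statistical analysis*). The plan gives no power calculation, SD or correlation, so there is no stated figure to reproduce. All correlations below are assumptions.

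**Is PCS available in both arms?** Item (7) does not itself say that every woman completed it. The general statements in the design section give the baseline surveys to all subjects and the same questionnaires to controls, so this is a fair reading. The survey list as a whole is described as repeated at the end, while item (7) mentions baseline only. Either way a baseline value exists.

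**Chance imbalance.** SE of the difference in arm-mean PCS = √(1/29 + 1/27) = 0.267 SD. About 32% of randomisations exceed one SE. This holds for any baseline variable, so it gives scale but is not evidence about this trial.

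**Gain from adding PCS to an ANCOVA that already has arm and the baseline outcome.** Let ρ be the partial correlation of PCS with the end score, given the baseline score. With 56 women, the variance ratio is (1 − ρ²) × 52/51, where 52/51 is the expected price of the extra covariate. Equivalent extra women = 56/ratio − 56.

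| Assumed ρ | Variance ratio | Change in variance | Equivalent extra women |
|---|---|---|---|
| 0 | 1.020 | 2% higher | −1 |
| 0.2 | 0.979 | 2% lower | 1 |
| 0.3 | 0.928 | 7% lower | 4 |
| 0.4 | 0.856 | 14% lower | 9 |

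Break-even is at ρ² = 1/52, so ρ = 0.14.

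**How PCS enters decides whether it helps.** Take the outcome SD as 1, and assume r = 0.5 (baseline with end score), 0.3 (PCS with baseline score) and 0.4 (PCS with end score).

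- *Planned arm-by-time test.* With two visits this is a comparison of change scores, with variance 2(1 − 0.5) = 1.000. A PCS main effect is the same at both visits and cancels. In a mixed model fitted to one simulated data set, the SE was 0.2137 with and without PCS.
- *The same test with a PCS-by-time term.* 1.000 − (0.4 − 0.3)² = 0.990. After the covariate price, 0.990 × 53/52 = 1.009, so the variance is about 1% higher.
- *ANCOVA on the baseline outcome.* 1 − 0.5² = 0.750. With its price, 0.750 × 53/52 = 0.764.
- *ANCOVA on the baseline outcome plus PCS.* R² = (0.25 + 0.16 − 2 × 0.5 × 0.4 × 0.3)/(1 − 0.09) = 0.29/0.91 = 0.319, leaving 0.681. With its price, 0.681 × 53/51 = 0.708.

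Against the planned test, the baseline outcome lowers the variance from 1.000 to 0.764, and PCS lowers it further to 0.708. The second step is 0.708/0.764 = 0.926, or 7% lower, which agrees with the table because these correlations imply ρ = 0.30. The detectable differences at 80% power (two-sided 0.05, allowing for lost degrees of freedom only) tell the same story: 0.763 SD for the planned test, 0.759 with PCS-by-time, 0.661 for ANCOVA, and 0.630 for ANCOVA plus PCS.

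**The intergroup comparison.** The plan also assesses intervention against control. If that means the end-of-study contrast alone, PCS would change its variance by (1 − 0.4²) × 53/52 = 0.856, about 14% lower. A simulation of 60,000 trials under the same correlations gave ratios of 1.009 (change score), 0.852 (end-score contrast) and 0.925 (ANCOVA), in line with the formulas.

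**The case against.** The strongest objection is that PCS has little to offer the contrast that is actually planned. Baseline pain and EHP-30 are already the first visit in the ANOVA, so any PCS imbalance that shifts both visits equally drops out of arm-by-time. A PCS main effect does nothing there, and a PCS-by-time term can cost slightly more than it returns. This stands. It is why the model must be named, and why the 2%, 7% and 14% figures apply to an ANCOVA and not to the plan as written.

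Prognostic value over three months in these women is also not shown. The plan's statement about PCS rests on a cited source, participants are already symptomatic and refractory to hormonal treatment, and the EHP-30 has its own control-and-helplessness scale that may overlap with PCS. This stands too, and is why ρ = 0 is included in the table.

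Finally, the trial is a preliminary-efficacy pilot and the covariate is optional. That limits the importance of the point. But the plan tests outcomes at p ≤ 0.05, and the adjustment uses data already collected.

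Two stronger readings are tempting. A reader might infer that omitting PCS biases the result or invalidates the analysis. The documents do not support that, because arms are randomised and the omission affects precision and chance imbalance only. A reader might also infer that adjustment removes the imbalance and the unexplained variance altogether. At ρ = 0.2 it lowers the variance by only 2%.

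**Conclusion.** The point holds as a low-priority improvement. A baseline measure that the plan itself treats as a risk marker is available in both arms, on a fair reading of the design section, and no outcome model uses it. The benefit ranges from a 2% loss to a 14% reduction in arm-effect variance for assumed partial correlations of 0 to 0.4, relative to an ANCOVA without PCS. None of these correlations can be checked from the documents. In the worked example the larger step, from 1.000 to 0.764, comes from conditioning on the baseline outcome, and PCS is a smaller addition to that. The case is strongest for pain and EHP-30, and the plan's description of PCS gives little support for extending it to cortisol.

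**What to change.** In *Statistical analysis*, state that for the pain (NRS, BPI) and EHP-30 outcomes the arm effect is estimated by ANCOVA of the end-of-intervention score on arm, the outcome's own baseline score and baseline PCS total. Enter PCS as a continuous 0–52 score, not cut at 30. Make the adjustment whatever the baseline comparison shows. Use only the baseline PCS, and fill a missing value with the overall mean so that no woman is dropped. Do not simply add PCS as a main effect to the two-visit repeated ANOVA.

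The plan is written in the past tense. If outcomes have already been analysed, present the adjusted result as a sensitivity analysis and label it so.

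The cost is a sentence or two in the SAP. Relative to an ANCOVA on the baseline outcome, PCS uses one further degree of freedom and raises the variance by about 2% if it proves uninformative.
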